6.1.3. Double-Blind Phase

Subjects who are stabilized and responding to their CAM2038 q1w dose (4, 8, 12, 16, 24, or 32 mg/week) at the end of the Titration Phase and who fulfill the pre-defined randomization criteria will be randomized to one of two treatment groups in the 12-week Double-Blind Phase:

- Group 1: CAM2038 q1w or CAM2038 q4w SC injections
- Group 2: placebo q1w or placebo q4w SC injections

During the Double-Blind Phase, all subjects who are receiving 4, 8 or 12 mg CAM2038 q1w at the end of the Titration Phase will be randomized to continue their respective CAM2038 q1w dosing of 4 mg, 8 mg or 12 mg CAM2038, or to matching placebo q1w for a total treatment duration of 12 weeks. Subjects who are receiving 16 mg, 24 mg or 32 mg CAM2038 q1w at the end of the Titration Phase will be randomized to CAM2038 q4w (64 mg, 96 mg or 128 mg, respectively) or to matching placebo q4w for a total treatment duration of 12 weeks.

Figure 1: Overview of Study Design

¹ One booster is allowed on Day 3-5 after the first CAM2038, 4 or 8 mg injection. If booster is taken, the next dose on week 2 will be 8 or 12 mg, otherwise stay at 8 mg. Then titration is weekly up to 10 weeks. Final Study Visit is 1 week after the last CAM2038 q1w dose for q1w subjects and 4 weeks after the last q4w dose for q4w subjects. Follow-up is within 4 weeks after the Final study visit.

IR = immediate release; MED=morphine equivalent dose; q1w=once weekly; q4w=once monthly; R= randomization. There will be a Final Study Visit or Early Termination and one Follow-up Call.

Rescue medication, hydrocodone/acetaminophen 5 mg/325 mg q4-6h prn, will be allowed during the Double-Blind Phase (up to three tablets or 15 mg/975 mg/day for subjects whose MED at screening was between 40-79 mg/day and up to six tablets or 30 mg/1950 mg/day for subjects whose MED at screening was ≥80 mg/day). Whenever subjects take rescue medication, they must record their pain intensity “at that moment” prior to taking rescue medication in the electronic diary.

6.1.4. Follow-up Phase for Subjects Not Transitioning to the Open Label Safety Extension Phase

A Final Study Visit will take place 1 week after the last CAM2038/placebo q1w dose or 4 weeks after the last CAM2038/placebo q4w dose. At the Final Study Visit (or early termination), subjects will be transitioned back to standard care or to their treatment prior to study entry. Subjects will then be contacted

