6.1.5. Open Label Safety Extension

Subjects who complete the Double-Blind Phase will be offered the opportunity to continue treatment in an open label safety extension for a total duration of up to 60 weeks. Subjects who consent to the Open Label Extension will not be required to participate in the post-double-blind Follow-up Phase but will be transitioned at their Final Study Visit or as soon as possible thereafter, to open label active treatment, in the Open Label Extension. With the Open Label Safety Extension Phase, total duration of exposure to CAM2038 is up to 60 weeks. Enrollment in the Open Label Safety Extension Phase will continue until a sufficient number of subjects have been recruited to obtain at least 52 weeks of safety information in approximately 100 subjects. Due to the double-blind design, all subjects will need to receive at least 1 week of CAM2038 q1w before proceeding to the Open Label Safety Extension Phase.

Subjects completing the Double-Blind Phase on 4 mg, 8 mg or 12 mg CAM2038/placebo q1w will continue on the same dose of active treatment (open-label CAM2038) without need for titration. Subjects completing the Double-Blind Phase on 64 mg, 96 mg or 128mg CAM2038/placebo q4w will begin open-label treatment at the corresponding equivalent weekly dose last received by the subject prior to transition to the monthly dosing regimen. The subject may transition to monthly dosing upon return to the clinic in 1 week following the initial dose. At the Investigator's discretion, the transition period may be extended or the patient down-titrated, in case of poor tolerability. The subjects will continue in the Open Label Safety Extension Phase until the total exposure to CAM2038 (including the Titration and Double-Blind Phases) is at least 52 weeks.

Once the required number of subjects for the Double-Blind phase of the trial has been recruited, enrollment for the Double-Blind phase will be closed, and remaining subjects offered the opportunity to proceed directly to the long-term safety extension without having to participate in a double-blind treatment phase. However, to be eligible to proceed to the safety extension, subjects must meet the following criteria:

- Have CAM2038 titrated to a dose that provides analgesia (i.e., 7-day mean $API \leq 4$)
- The dose of CAM2038 is well-tolerated for 7 days before randomization (no adverse effects that require a change in study dosing or interruption)

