8.1.7.1. Dosing Schedule

The dose titration schedule below provides guidance regarding titration of subject dosing upon enrollment into the open label extension portion of the study following participation in the double-blind randomization.

- All subjects will be started on the weekly CAM2038 regimen during the open label extension.
- Subjects completing the randomized double-blind phase on 4 mg, 8 mg, or 12mg CAM2038/placebo q1w will continue the same dose of active treatment (open label CAM2038) without need for titration.
- Subjects completing the randomized double-blind phase on 64 mg, 96mg, or 128mg CAM2038/placebo q4w will begin open label treatment at the corresponding equivalent weekly dose last received by the subject prior to transition to the monthly dosing regimen. The subject may transition to monthly dosing upon return to the clinic in 1 week following the initial dose. At the investigator’s discretion, the transition period may be extended or the patient down-titrated, in case of poor tolerability.
- Additional details are presented in [Table 4](#) below:

Table 4 Open-Label Extension Dose Schedule for Randomized Double-Blind Rollover

Randomized Double-Blind Dose	Titration Schedule
4mg CAM2038 q1w	Remain at 4mg weekly
8mg CAM2038 q1w	Remain at 8mg weekly
2mg CAM2038 q1w	Remain at 12mg weekly
64mg monthly*	Start at 16mg q1w
96mg monthly*	Start at 24mg q1w
128mg monthly*	Start at 32mg q1w

*Please note:

- 16 mg CAM2038 q1w is the dosing equivalent of 64 mg CAM2038 q4w
- 24 mg CAM2038 q1w is the dosing equivalent of 96 mg CAM2038 q4w

- 32 mg CAM2038 q1w is the dosing equivalent of 128 mg CAM2038 q4w

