8. PRIOR AND CONCOMITANT MEDICATIONS

All medications recorded on the CRFs will be coded using the WHO Drug Dictionary. Prior and concomitant medications will be summarized by treatment arm in the Safety Population by Anatomical Therapeutic Chemical Class Level 4 and WHO Drug base substance preferred name.

Prior medications are defined as medications with stop dates occurring before the date of first administration of any study medication. Concomitant medications are defined as medications with start dates occurring on or after the date of first administration of any study treatment component and no more than 30 days after the last administration of any study treatment component. Medications with start and stop dates that bracket the date of first administration of any study treatment component will be summarized as both prior and concomitant medications.

Prior and concomitant medication will be summarized for both Primary and Supportive Safety Populations.

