10.2 ADVERSE EVENTS

All AE and serious adverse event (SAE) terms recorded on the CRFs will be coded by primary system organ class (SOC) and will be mapped to a preferred term using the MedDRA. The Investigator will assess AE severity and relationship to the study treatment.

A treatment-emergent adverse event (TEAE) is defined as any AE with an onset date on or after the first dose of CAM2038, or any ongoing event on the date of first dose that worsens in severity after the first dose of CAM2038. Only TEAEs with an onset date prior to date of last dose plus 30 days will be tabulated in summary tables. For the purpose of calculating TEAEs and inclusion in summary tables, incomplete onset dates will be imputed as detailed in Appendix A.

AEs will be summarized by the number and percent of subjects in each primary SOC and preferred term, and subjects will be counted only once for each primary SOC and each preferred term. Summary tables of AEs by primary SOC, preferred term, and intensity will be provided. If a subject has more than one AE coded to the same preferred term, the subject will be counted only once for that preferred term by using the event with the highest intensity. Similarly, if a subject has more than one AE within a primary SOC category, the subject will be counted only once in that SOC category by using the event with the highest intensity.

AEs by primary SOC, preferred term, and relationship to study drug will be provided as well. If a subject has more than one AE coded to the same preferred term, the subject will be counted only once for that preferred term by using the most related event. Similarly, if a subject has more than one AE within a primary SOC category, the subject will be counted only once in that primary SOC category by using the most related event.

In addition, SAEs by primary SOC and preferred term will be provided. Deaths and SAEs will be summarized similarly to AEs. All adverse event tables will also include the total number of events, counting multiple events per subject.

AEs, Injection-related AEs, and other (non-injection related) AEs will be presented by treatment group and overall. Summaries of these AE subsets will be presented for the following categories:

- Study drug related AEs
- AEs by intensity
- AE relationship to injection
- Possibly study drug related AEs, by intensity
- AEs reasonably related to injection, by intensity
- SAEs
- AEs that led to discontinuation
- SAEs that led to discontinuation

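### The double-blind adverse event window (last dose plus 30 days) has no stop at the first open-label extension injection, so for weekly subjects who roll over promptly it takes in about 23 days on open-label CAM2038

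*SAP*

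**What the plan says.** SAP 10.2 opens the window at titration: "A treatment-emergent adverse event (TEAE) is defined as any AE with an onset date on or after the first dose of CAM2038". It closes it for the summary tables with "Only TEAEs with an onset date prior to date of last dose plus 30 days will be tabulated in summary tables". Neither sentence mentions the extension, and *last dose* is not defined. SAP 8 uses a parallel limit for concomitant medications: "no more than 30 days after the last administration of any study treatment component".

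Protocol 6.1.4 fixes the end of double-blind treatment: "A Final Study Visit will take place 1 week after the last CAM2038/placebo q1w dose or 4 weeks after the last CAM2038/placebo q4w dose". Under Protocol 6.1.5, subjects who consent to the extension "will be transitioned at their Final Study Visit or as soon as possible thereafter, to open label active treatment, in the Open Label Extension". The footnotes to Figure 2 allow up to 28 days between the two phases. Week 23 is the Final Study Visit in Table 6 and also the first extension injection visit in Table 8a.

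Protocol 8.1.7.1 applies to former placebo subjects too: "All subjects will be started on the weekly CAM2038 regimen during the open label extension". Those on the 4, 8 or 12 mg weekly levels, active or placebo, "will continue the same dose of active treatment (open label CAM2038) without need for titration".

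SAP 3 limits the plan to the titration and double-blind phases and leaves the extension to a separate SAP. SAP 5.4 and SAP 10 group safety data by treatment or study drug received. SAP 10.1 counts exposure up to 1 week after the last weekly injection or 4 weeks after the last monthly one.

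**The concern.** A 30-day tail is meant to catch late events from the treatment just stopped. Here, for a subject who rolls over, a new treatment starts inside the tail, and what that means differs by arm. A former active subject continues the same drug. A former placebo subject restarts CAM2038 after 12 weeks without it. If the rule is programmed as written, events from that restart meet the cut-off and fall in the column of the double-blind treatment, placebo.

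The tables affected are those SAP 10.2 presents by treatment group: drug-related, injection-related and serious events, events leading to discontinuation, and terms reaching 5% in any group. Drug events counted under placebo make the two columns look more alike and so understate harm. The effect would sit almost wholly in the weekly stratum. The events will be in the database, since Protocol 9.5.1 collects adverse events until the final follow-up.

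**Working it through.** The cut-off is a rule, so there is no figure of the plan's to reproduce. The check has two parts.

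**1. Length of the overlap**

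Take *last dose* as the last double-blind injection. Onset before last dose + 30 means day offsets 0 to 29. With g the number of days from that injection to the first extension injection, overlap = max(0, 30 − g).

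| Regimen | Last double-blind dose | Last day in window | First extension dose, nominal | Overlap, nominal | Overlap, visit windows |
|---|---|---|---|---|---|
| Weekly | Day 78 | Day 107 | Day 85 (g = 7) | 30 − 7 = 23 days | g = 4 to 10 (±3 days, Table 6): 26 to 20 |
| Monthly | Day 57 | Day 86 | Day 85 (g = 28) | 30 − 28 = 2 days | g = 21 to 35 (±7 days, Table 7): 9 to 0 |

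As a share of the post-randomization window: weekly 23/107 = 21%, monthly 2/86 = 2%. A further delay before the extension of 23 days (weekly) or 2 days (monthly) brings the overlap to zero. The permitted gap is 28 days, so this can happen in either regimen.

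The 23 days are also the amount by which the 30-day tail exceeds the 1-week tail that SAP 10.1 uses for weekly exposure (30 − 7).

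**2. Share of placebo-column events occurring on CAM2038**

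The documents give neither a rollover rate nor a regimen split. Protocol 7 plans about 140 extension subjects in total. If all were rollovers split evenly by arm, 70 of 170 placebo subjects would roll over, r = 70/170 = 0.41. De novo subjects count toward the 140, so this is roughly the most the plan implies. Assume a weekly share w = 0.5, immediate rollover, and an event rate on restart rr times the placebo rate.

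- Mean overlap per rollover: 23 × 0.5 + 2 × 0.5 = 12.5 days.
- Event weight on CAM2038: r × rr × 12.5.
- Event weight off CAM2038: 84 + (1 − r) × 12.5.
- Share = weight on / (weight on + weight off).

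| r | Weight off | rr = 1 | rr = 2 | rr = 3 |
|---|---|---|---|---|
| 0.41 | 84 + 0.588 × 12.5 = 91.4 | 5.1/96.5 = 5% | 10.3/101.6 = 10% | 15.4/106.8 = 14% |
| 0.20 | 84 + 0.80 × 12.5 = 94.0 | 2.5/96.5 = 3% | 5.0/99.0 = 5% | 7.5/101.5 = 7% |

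These are shares of events after randomization. If titration days stay in the same table, as the opening rule in SAP 10.2 allows, the denominator grows and the shares fall. The incidence tables count a subject once per term, so incidence moves less wherever the term had already occurred in that subject.

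**The case against.** The strongest reply is that the SAP never says restart events go under placebo. SAP 3 confines the plan to the phases before the extension, Protocol 11.1 and 11.2 give the extension its own SAP and Safety Population, and tables are by drug received. A programmer could reasonably drop these events. That stands as far as it goes: placebo placement is the literal reading of the cut-off and not stated text, so a reader who infers that the plan deliberately counts restart events under placebo goes beyond the documents. But a scope statement is not a cut-off date, and grouping by treatment received does not say how to classify one subject who had placebo and then open-label drug. The other readings of *last dose* do not help. The last dose of any study drug would bring in the whole extension. The last CAM2038 dose before the extension would close the placebo window 30 days after titration.

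Four further limits also stand:

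- The monthly overlap is close to nothing.
- Rollover may come later than the Final Study Visit, which shortens or removes the overlap.
- Rollover of 60% or 80% among placebo subjects would need 102 or 136 of the roughly 140 planned extension places from that arm alone, so larger contamination figures built on such rates do not fit the plan.
- SAP 10 has no pre-specified safety outcome and calls formal between-arm comparisons post hoc, so what is affected is descriptive.

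Double reporting under the extension SAP cannot be judged, because that document is not available.

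**Conclusion.** The concern holds in a limited form. SAP 10.2 states a closing rule that, followed as written, runs into the extension for subjects who roll over promptly, and nothing elsewhere stops it. The overlap is material for weekly subjects (23 days, 20 to 26) and minor for monthly ones (2 days, 0 to 9). The likely direction is a narrower active–placebo contrast in the descriptive harms tables. Its size is about 5% to 14% of post-randomization placebo-column events at the planned upper bound on rollover, and about 3% to 7% at 20% rollover. These figures rest on an assumed even regimen split, immediate rollover, and rate ratios of 1 to 3.

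The documents do not support the stronger inference that the placebo column will certainly contain these events or that harms will be badly understated. They do support correcting the rule before the tables are produced, because the outcome otherwise depends on an unwritten programming decision.

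**What to change.** In SAP 10.2, for the double-blind tables:

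- Define *last dose* as the last double-blind injection.
- End each subject's window at the earlier of that dose plus 30 days and the first open-label extension injection.
- Report later events only under the extension SAP.
- Apply the same cut to concomitant medications in SAP 8.

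This takes a short SAP revision and one date condition in each program. The extension injection times are already recorded (footnotes to Tables 8a and 8b).

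The cost to state openly is that weekly rollovers keep about 7 post-dose days against 30 for subjects who do not roll over. Only completers can roll over from the double-blind phase, so length of post-treatment follow-up becomes linked to completion. A supportive table limited, for all subjects, to the SAP 10.1 exposure period (1 week after the last weekly injection, 4 weeks after the last monthly one) would put rollovers and others on an equal footing.

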10.3 LABORATORY ASSESSMENTS

Chemistry, hematology, urinalysis and coagulation profiles will be assessed (see Protocol Section 9.5.9 for a complete list of parameters to be assessed). Summary statistics for these parameters will be presented by visit for the actual value and change from baseline for each test in each laboratory category (hematology, chemistry, urinalysis and coagulation profile). Shift tables will be presented for shifts from baseline lab categories to end-of-study laboratory category. The three laboratory categories will be: L (below lower bound of normal range), N (within normal range) and H (above higher bound of normal range).

If a lab value is reported using a non-numeric qualifier (e.g., less than [$<$] a certain value, or greater than [$>$] a certain value), the given numeric value will be used in the summary statistics, ignoring the non-numeric qualifier.

If a subject has repeated laboratory values for a given timepoint, the value from the first evaluation at that timepoint will be used for summary purposes. For the purpose of determining baseline, the last non-missing observation on or prior to randomization will be used.

10.4 VITAL SIGNS

For the purposes of this SAP, vital signs will consist of blood pressure (systolic and diastolic blood pressure, mm Hg), pulse rate (beats per minute), respiratory rate (breaths/minute) and oxygen saturation (%), collected while sitting, following a rest period of at least 3 minutes. Vital signs values and change from baseline in the vital signs will be summarized for each treatment group.

10.5 PHYSICAL EXAMINATIONS

Number and percent of subjects with abnormal physical exam findings at Screening will be summarized by body system for each treatment group and overall. Physical examinations data for each subject will also be presented in a listing.

10.6 12-LEAD ELECTROCARDIOGRAM (ECG)

Twelve-Lead ECGs will be assessed after the subject has been resting in a recumbent/supine position for at least 3 minutes (see Protocol Section 9.5.11 for a complete list of parameters to be assessed). The ECG variables will include ventricular heart rate and the PR, QRS, QT, QTcB and QTcF intervals. The ECGs

will be signed and dated by a medically qualified individual; he or she will confirm review of the ECG and verify whether any abnormalities are clinically significant.

Number and percent of subjects in each ECG finding category (normal; abnormal not clinically significant; and abnormal and clinically significant) will be summarized for each visit by each treatment group and overall. Summary statistics will be presented for the actual value and change for each ECG parameter.

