This is a Phase III, placebo-controlled, multicenter study with an enriched-enrollment withdrawal (EEW) design to evaluate the efficacy and safety of CAM2038 in opioid-experienced subjects with moderate to severe CLBP that requires continuous, around-the-clock (ATC) opioid treatment ≥ 40 mg morphine equivalent dose (MED). The study includes 5 phases: A Screening Phase (up to 2 weeks), a Transition Phase (up to 2 weeks), an Open-Label Titration Phase (up to 10 weeks), a Double-Blind Treatment Phase including a Final Study Visit (12 weeks), and a Follow-up Phase (4 weeks). The overall duration of participation in the core phase of the study (randomized Double-Blind Phase) is up to 30 weeks, from the Screening Phase through the Follow-up Phase.

Subjects will record their API at Screening and prior to the test dose on a paper diary at the site. Throughout the study, after subjects receive their first CAM2038 injection, they will record their WPI and API using the NRS-11 in an electronic diary. Subjects will be instructed to record their WPI and API once daily between 18:00 and 23:59 (i.e., 6:00 pm and 11:59 pm). Subjects will be instructed to make all attempts to record their pain scores at the same time of day throughout the study. In addition, subjects will be instructed to record their pain intensity in the electronic diary on the NRS-11 “at that moment” prior to taking rescue medication. Rescue medication use will also be recorded in the electronic diary.

Following screening and confirmation of eligibility, subjects will enter a Transition Phase of up to 2 weeks during which their current opioid dose will be down-titrated by approximately 25% per day to:

- ≤ 80 mg/day MED (for subjects whose opioid dose at screening is > 80 mg/day MED)
- or to ≤ 40 mg/day MED (for subjects whose opioid dose at screening is between 40 mg/day and 79 mg/day MED).

Following the down titration, subjects will be transitioned to an immediate-release (IR) morphine for at least 2 days before they enter the Open-Label Titration Phase, as follows:

- 15 mg 4 times daily [QID] for subjects whose MED at screening was ≥ 80 mg/day
- 15 mg 3 times daily (TID) for subjects whose MED at screening was 40-79 mg/day.

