9.5.12. Physical Examination

A complete physical examination, including all major body systems (and height, weight, and BMI) will be performed at Screening and at the Final Study Visit/Early Termination.

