11.3.7. Analysis of Safety

Exposure will be summarized by treatment group.

AEs will be coded by primary system organ class (SOC) and preferred term according to the Medical Dictionary for Regulatory Activities and summarized by number and percent of subjects in each primary SOC and preferred term. Summaries of these AE subsets will be presented for relationship to study drug, intensity, seriousness, AEs or SAEs leading to discontinuation, and AEs occurring in 5% or greater of any treatment group (by preferred term). Frequencies for deaths and hospitalizations will also be summarized

by treatment group and overall.

Data for clinical laboratory tests, ECG, COWS/SOWS, vital signs, injection site reactions, and physical examinations will be summarized using standard descriptive and change from baseline statistics. Shift tables and tabular summaries of abnormalities will be provided, where appropriate.

Medications will be coded using the WHO Drug Dictionary and summarized using descriptive statistics.

By-subject listings will be provided for all safety data.

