10. SUMMARIES OF MEASURES OF SAFETY

Safety analyses will be performed for both the Primary and Supportive Safety Populations. Safety evaluations will be based on the incidence, intensity, and type of adverse events (AEs), as well as on clinically significant changes in the subject's physical examination, vital signs, electrocardiogram (ECG), clinical laboratory results, and injection site examination. Safety variables will be tabulated and presented by study drug received.

Because there is no pre-specified safety outcome defined in terms of AEs, clinically relevant laboratory parameters, or vital signs in the Double-Blind Treatment Phase of the study, any formal comparisons between the treatment arms with respect to specific safety parameters will be post hoc.

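### SAP 10.5 tabulates physical examination findings by arm at Screening only, so the examination done after treatment has no by-arm summary

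*SAP*

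**What the plan says.** SAP 10.5 consists of two instructions. The first defines a table: "Number and percent of subjects with abnormal physical exam findings at Screening will be summarized by body system for each treatment group and overall". The second defines a listing: "Physical examinations data for each subject will also be presented in a listing". No other physical examination output is specified.

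Protocol 9.5.12 says that a complete examination, covering all major body systems and height, weight and BMI, "will be performed at Screening and at the Final Study Visit/Early Termination". The schedules agree: Table 5 places it at Screening, and Tables 6 and 7 place it at the Final Study Visit.

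Protocol 11.3.7 names the examination alongside laboratory tests, ECG, vital signs and other safety data, and says that "physical examinations will be summarized using standard descriptive and change from baseline statistics". It then adds: "Shift tables and tabular summaries of abnormalities will be provided, where appropriate".

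The introduction to SAP Section 10 rests safety evaluation on adverse events "as well as on clinically significant changes in the" physical examination, vital signs, ECG, laboratory results and injection site. It also says: "Safety variables will be tabulated and presented by study drug received".

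**The concern.** A table of abnormal findings split by treatment group looks like a safety comparison, but this one uses data from before treatment. At Screening no subject has had CAM2038 or been randomised, so any difference between the arms in that table arises by chance. The examination that could carry information about treatment is the later one, and it is given no table.

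At stake is whether safety reporting is complete. Followed exactly, the plan does not produce the change-from-baseline summary of physical examinations that the protocol commits to. A reader of the study report who wanted to know whether new abnormal findings were more frequent in one arm, or whether weight moved differently, would have to count from listings.

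**Working it through.** There is no stated figure to reproduce, and the point depends on no power, variance or dropout assumption. The check sets the passages side by side and counts timepoints.

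**1. Timing of the tabulated examination.** The protocol synopsis gives the order: "Following screening and confirmation of eligibility, subjects will enter a Transition Phase of up to 2 weeks". IR morphine, the Buprenex test dose, CAM2038 titration and randomisation all come later. The Screening examination therefore precedes all study drug.

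**2. Count of examinations.** In the core study:
- scheduled: 2 (Screening; Final Study Visit or early termination)
- tabulated by SAP 10.5: 1 of 2 (Screening)
- post-exposure examinations tabulated: 0 of 1

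**3. Comparison with neighbouring SAP sections.**

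| Data | Post-baseline summary in the SAP |
|---|---|
| Laboratory (10.3) | By-visit values and changes; shifts from baseline to end of study |
| Vital signs (10.4) | Values and change from baseline |
| ECG (10.6) | Finding categories at each visit; values and changes |
| Injection site (10.7) | Results summarised and listed |
| Physical examination (10.5) | None; listing only |

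Section 10.5 is the exception in this group, and the SAP gives no reason for it.

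**4. Weight.** Protocol 9.5.12 collects weight and BMI as part of the examination. The vital signs in SAP 10.4 do not include weight, and SAP 7.2 uses BMI only as a baseline characteristic. No SAP section summarises weight after treatment, although it is a numeric variable to which a change from baseline applies directly.

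**5. Other routes to a by-arm table.** Protocol 9.5.1 asks for clinically significant abnormal examination findings to be reported as adverse events if they first appear during the study, or if they were present at Screening and then worsen significantly. SAP 10.2 tabulates adverse events by arm. A clinically significant new or worsened finding should therefore be counted, as an adverse event. A finding judged not clinically significant has no such route.

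**6. What a shift from Screening would span.** Tables 5 to 7 show no physical examination at randomisation, so Screening is the only available reference. The maximum interval to the Final Study Visit is 2 weeks (Screening) + 2 (Transition) + 10 (Titration) + 12 (Double-Blind) = 26 weeks. Both arms take CAM2038 during the up to 10 weeks of titration, and the arms differ only in the last 12 weeks. The default baseline in SAP 6.1 is the day of randomisation, which does not fit this variable, so 10.5 would need to name Screening as its baseline.

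**The case against.** The strongest defence is the adverse event route. Section 10 of the SAP speaks of clinically significant changes, and Protocol 9.5.1 sends exactly those changes to the adverse event tables. On that reading Section 10 is largely honoured without an examination table. Much of this stands, and it is why the point is minor. It does not settle the matter: the route depends on the investigator's judgement of significance, and Protocol 9.5.1 covers laboratory and ECG findings in the same way, yet the SAP still tabulates those.

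A second defence is that the protocol commitment is soft. It is one generic sentence covering many data types, shift tables are promised only where appropriate, numeric change statistics do not suit normal/abnormal findings, and Protocol 11.1 lets the SAP amend the planned analyses. This is fair as far as it goes. But 10.5 does not say that it amends anything, an abnormality table is the natural form for such data, and weight is numeric. SAP 10.2 leaves room for further safety analyses, and Section 10 says that safety variables will be tabulated, but neither specifies a final-visit examination table, whereas 10.5 names Screening.

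A reader might infer more than the documents support:
- *That the final examination enters no safety summary at all.* Clinically significant findings should appear among the adverse events.
- *That a difference in injection-area findings would go untabulated.* SAP 10.7 summarises injection-site examinations, which Protocol 9.5.13 requires at each scheduled visit.
- *That some 340 examinations go unsummarised.* That is the randomisation target. Protocol 7.7 recognises that early termination procedures may be refused, and SAP 5.4 excludes Sites 068 and 077 from the primary safety summaries.

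**Conclusion.** The point holds as a minor one. SAP 10.5 states a definite rule with the wrong timepoint: it yields a by-arm safety table that cannot show a treatment effect and leaves the informative examination to a listing. This conflicts with Protocol 11.3.7. With the introduction to SAP Section 10 the fit is poor rather than contradictory, because of the adverse event route.

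In size, one of two scheduled examinations is tabulated and none after exposure. The information without a by-arm table is the examination result itself, mainly findings judged not clinically significant, together with change in weight. The data are not lost, since they are listed. The primary efficacy analysis is not touched.

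The limited size assumes that investigators report clinically significant findings as adverse events as Protocol 9.5.1 requires. If that reporting were incomplete, the missing table would matter more.

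**What to change.** Keep the Screening table in 10.5 and label it as a baseline description. Add, for the Primary and Supportive Safety Populations:

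- A full shift table from Screening to the Final Study Visit or early termination, by body system and treatment group. It should show every combination of Screening and final status, not only normal to abnormal, with counts of missing final examinations. If severity or clinical significance is recorded, use those categories, so that worsening of a finding already abnormal at Screening is visible.
- A descriptive summary of weight and its change from Screening, by treatment group.
- A statement that Screening is the baseline for this variable, and a footnote that the shift spans the open-label titration period, when both arms received CAM2038.

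The cost is minor programming on data already scheduled for collection. No additional visits or assessments are needed.
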